6.1. Inclusion Criteria

Participants will be eligible for inclusion in this study only if all of the following criteria apply at **screening (Week -4 and Week -2)** and **randomization (Day 1)**, unless otherwise specified:

Age

1. ≥ 18 years of age at the time of signing the informed consent.

Type of Participant and Disease Characteristics

2. **CKD:** Have CKD, confirmed at screening: Kidney Disease Outcomes Quality Initiative (KDOQI) CKD stages 3, 4, or 5 defined by Estimated glomerular filtration rate (eGFR) using the CKD Epidemiology Collaboration (CKD-EPI) formula [Levey, 2009].
3. **Hgb:** Stable HemoCue Hgb from 8.5 to 10.5 at screening visit (Week -4) and from 8.5 to 10.0 g/dL at randomization (Day 1) (Section 9.1).
4. **IV Iron:** Participants may receive up to one IV iron dose within the 8 weeks prior to screening and NO IV iron use between screening visit and randomization (Day 1).
5. **Oral Iron:** If needed, participant may be on stable maintenance oral iron supplementation. There should be $<50\%$ change in overall dose and no change in type of iron prescribed doses in the 4 weeks prior to Day 1 randomization visit.

Sex

6. Male and female participants are eligible. A female participant is eligible to participate if she is not pregnant (see Section 12.4), not breastfeeding, and at least one of the following conditions applies:
 - Not a woman of childbearing potential (WOCBP) as defined in Section 12.4 (Appendix 4), or
 - A WOCBP who agrees to follow the contraceptive guidance in Appendix 4 during the treatment period and for at least 4 weeks after the last dose of study treatment.

Informed Consent

7. Capable of giving signed informed consent as described in Section 12.2 Appendix 2 which includes compliance with the requirements and restrictions listed in the informed consent form (ICF) and in this protocol.

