5.2. Baseline Definitions and Derivations

5.2.1. Baseline Definitions

For all endpoints the baseline value will be the latest non-missing pre-dose assessment on or before the randomization date (except as noted below). This is generally expected to be the pre-dose value from the Day 1 visit, although such values may be missing.

| Parameter | Study Assessments Considered As Baseline | | | Baseline Used in Data Display |
|---|--|----------------|------------------|-------------------------------|
| | Screen Week -4 | Screen Week -2 | Day 1 (Pre-Dose) | |
| Efficacy | | | | |
| Hgb ^[1] | | | X | Day 1 |
| Iron Parameters | | | X | Day 1 |
| Monthly Oral iron ¹ | | | X | Day 1 |
| Monthly IV iron ² | | | X | Day 1 |
| Estimated Glomerular Filtration Rate (eGFR) | | | X | Day 1 |
| Serum Creatinine | | | X | Day 1 |
| Safety | | | | |
| SBP/DBP and HR | | | X | Day 1 |
| Lipid Parameters, Clinical Chemistry, Hematology, Other Laboratory, and Hepatobiliary (liver) Tests | | | X | Day 1 |
| PRO | | | | |
| Actigraphy | | | X | Day 1 |
| SF-36 Domain and | | | X | Day 1 |

CONFIDENTIAL

205270

| Parameter | Study Assessments Considered As Baseline | | | Baseline Used in Data Display |
|------------------|--|----------------|------------------|-------------------------------|
| | Screen Week -4 | Screen Week -2 | Day 1 (Pre-Dose) | |
| Component Scores | | | | |
| CKD-AQ | | | X | Day 1 |
| WPAI-ANS-CPV | | | X | Day 1 |
| EQ-5D-5L & VAS | | | X | Day 1 |
| PGI-S | | | X | Day 1 |
| PGI-C | | | X | Day 1 |

NOTES:

- Unless otherwise stated, the mean of replicate assessments at any given time point will be used as the value for that time point.

[1] Baseline monthly oral iron dose will be defined as total oral iron (mg) over the 4 weeks prior to randomization. See Section 10.6.3.

[2] Baseline IV monthly iron dose will be defined as total IV iron (mg) over the 8 weeks prior to screening, since participants may only receive up to one IV iron dose within the 8 weeks prior to screening and no IV iron use between screening visit and randomization. See Section 10.6.3.

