| 
 • Hepcidin, ferritin, and serum iron on-treatment values will be log-transformed (see Section 5.2.2) and summarized using geometric mean, coefficient of variation, minimum, P25, median, P75, and maximum for each scheduled visit by treatment group. Graphical summaries will be provided. • TSAT and TIBC on-treatment values will be summarized using mean, standard deviation, minimum, P25, median, P75, and maximum for each scheduled visit by treatment group. Graphical summaries will be provided. • Percent change from baseline in log-transformed (see Section 5.2.2) hepcidin, ferritin, and serum iron on-treatment values will be summarized using geometric mean, coefficient of variation, minimum, P25, median, P75, and maximum for each scheduled visit by treatment group. Graphical summaries will be provided. • Change from baseline in TSAT and TIBC on-treatment values will be summarized using mean, standard deviation, minimum, P25, median, P75, and maximum for each scheduled visit by treatment group. Graphical summaries will be provided. • Average monthly oral or IV iron dose (mg)/participant to Week 28 will be determined by calculating the total elemental oral or IV iron dose per participant from Day 1 to Week 28 while the participant was on randomized treatment and dividing by (the number of days the participant was on randomized treatment/30.4375 days). (see Section 10.6.3) • Average monthly oral iron dose/participant and average monthly IV iron dose/participant at baseline, and while on treatment to Week 28 will be summarized by treatment group (see Section 10.6.3). Summaries will include mean, standard deviation, minimum, P25, median, |

CONFIDENTIAL

205270

P75, and maximum by treatment group.

- The number and percentage of participants that reduced oral iron supplementation relative to baseline during the EP and during the treatment period while on treatment will be summarized by treatment group (see Section 10.6.3).
- The number and percentage of participants who required IV iron during study treatment (day 1 to week 28) will be summarized by treatment group.

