| 
 Only defined for participants with a non-missing treatment start date Hgb, iron parameters, oral iron, PRO and Actigraphy: the latest value on or before the treatment stop date + 1 day. Blood pressure, central laboratory, and vital signs parameters: the latest value on or before the last non-zero dose date + 1 day, or if the last non-zero dose date is missing, the study completion date for participants who have a non-missing treatment start date. |
| Study Completion/Withdrawal Date |
| 
 Date of withdrawal for participants withdrawing (i.e., participants who actively withdraw or are deemed lost to follow-up) from study or date of completion of study for participants who complete the study. Note: Participants who die while on study are considered as having completed the study |
| Treatment Day |
| 
 Calculated as the number of days from treatment start date: 
 Treatment Start Date = Missing → Treatment Day = Missing Ref Date < Treatment Start Date → Treatment Day = Ref Date – Treatment Start Date Ref Date ≥ Treatment Start Date → Treatment Day = Ref Date – (Treatment Start Date) + 1 |
| First Study Contact Date |
| 
 First study contact with the participant while on the study |
| Last Study Contact Date |
| 
 Last study contact with participant (clinic, telephone or other contact with participant) with the participant while on the study |
| Time Definitions (per GSK standard principles) |
| 
 1 week = 7 days 1 month = 30.4375 days 1 year = 365.25 days |
| Production of Two-Sided p-values |
| 
 The majority of the efficacy and safety analyses in this study will use one-sided 2.5% p-values assess statistical significance. Should two-sided p-values be required for publication purposes after the study is complete, the corresponding two-sided p-values will be produced at that time. |

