| 
 • The calculation of the average monthly oral iron from Randomization to Week 28 will follow the calculation of the average monthly IV iron from Randomization to Week 28 in Section 10.6.3 below. |
| Average Monthly Oral Iron from Week 24 to Week 28 |
| 
 • The calculation of the average monthly oral iron from Week 24 to Week 28 will follow the calculation of the average monthly IV iron from randomization to Week 28 in Section 10.6.3 below, except randomization date will be replaced with Week 24 date. |
| Reduction in Oral Iron Supplementation |
| 
 • A reduction in Oral iron supplementation relative to baseline occurs when Baseline average monthly oral |

CONFIDENTIAL

205270

| Iron Endpoints | | | | | | | | | | | | | | | | | | | | | | | | | | | | | | | | | | | | | | | | | | |
|---|--|--|-------------------|------------------|---|----------|------------------|---|-----------|------------------|---|----------|------------------|---|---------|-----|----|--------|------------|---|--------|---------------|-----------|-----|----------------|----|--------|---------------|-----|---------|---------------|------|---------|--------------|------|---------|-------------|---|--------|-----|----|--------|
| iron > EP average monthly oral iron, when both baseline oral iron and EP average monthly oral iron are non-missing. | | | | | | | | | | | | | | | | | | | | | | | | | | | | | | | | | | | | | | | | | | |
| Baseline Average Monthly IV Iron | | | | | | | | | | | | | | | | | | | | | | | | | | | | | | | | | | | | | | | | | | |
| 
 Participants may receive up to one IV iron dose within the 8 weeks prior to screening and no IV iron use between screening visit and randomization (Day 1) If no IV iron was used within the 8 weeks prior to screening, the baseline monthly IV iron dose is 0; otherwise the recorded one IV iron dose is the baseline monthly IV iron dose. | | | | | | | | | | | | | | | | | | | | | | | | | | | | | | | | | | | | | | | | | | |
| Average monthly IV iron from Randomization to Week 28 | | | | | | | | | | | | | | | | | | | | | | | | | | | | | | | | | | | | | | | | | | |

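### The monthly baseline iron doses are unscaled 8-week (IV) and 28-day (oral) amounts, while on-treatment iron is scaled to a 30.4375-day month, so the two are not comparable

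*SAP*

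**What the plan says.** - **Month length.** SAP 10.6.1 fixes "1 month = 30.4375 days".
- **Baseline IV iron.** SAP 5.2.1: "Baseline IV monthly iron dose will be defined as total IV iron (mg) over the 8 weeks prior to screening". The reason given is eligibility: "since participants may only receive up to one IV iron dose within the 8 weeks prior to screening". This follows Protocol 6.1, criterion 4: "Participants may receive up to one IV iron dose within the 8 weeks prior to screening", with none allowed from screening to Day 1. SAP 10.6.3 agrees: with no dose the baseline is 0, "otherwise the recorded one IV iron dose is the baseline monthly IV iron dose". No divisor is applied in either place.
- **Baseline oral iron.** SAP 5.2.1: "Baseline monthly oral iron dose will be defined as total oral iron (mg) over the 4 weeks prior to randomization". SAP 10.6.3 repeats this.
- **On-treatment iron.** SAP 7.4.2 converts the total oral or IV dose from Day 1 to Week 28 to a monthly average by "dividing by (the number of days the participant was on randomized treatment/30.4375 days").
- **Display.** SAP 7.4.2, on the planned summary: "Average monthly oral iron dose/participant and average monthly IV iron dose/participant at baseline, and while on treatment to Week 28 will be summarized by treatment".
- **Oral reduction rule.** SAP 10.6.3 counts a participant as having reduced oral iron when the baseline monthly dose exceeds the monthly average in the evaluation period (EP).
- **A second IV baseline formula.** Also in SAP 10.6.3, the derivation of average monthly IV iron from randomization to Week 28 ends with a weighted mean labelled as the baseline monthly IV dose. Its divisor is (16 × 7)/30.4375. The EP oral calculation is referred to this same derivation, with the Week 24 date in place of randomization.

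**The concern.** Baseline and on-treatment values carry the same monthly label and are planned for the same summary, but under 5.2.1 and 7.4.2 they are in different units. The IV baseline covers about 1.84 SAP months and the oral baseline about 0.92, whereas the on-treatment values are per SAP month.

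A reader judging whether treatment spares iron will compare baseline with on-treatment use within an arm. The two mismatches run in opposite directions. Together they could suggest a shift from IV to oral iron when nothing changed. The oral mismatch also enters a defined exploratory endpoint, the number of participants who reduced oral iron, during the EP (Table 2.103) and during the treatment period (Table 2.104).

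**Working it through.** The SAP states no resulting percentage to reproduce. Its month convention does check: the once-a-month frequency of 0.23 per week in SAP 10.6.3 equals 7/30.4375 = 0.230.

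**Inputs.** Month M = 30.4375 days (10.6.1); IV window 56 days and oral window 28 days (5.2.1); treatment period 28 × 7 = 196 days; on-treatment average = total/(days/M) (7.4.2). D is one IV dose and d a constant daily oral dose.

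**IV iron, use unchanged, 7.4.2 scaling.** The baseline as defined is D. At one dose per 8 weeks, 28 weeks hold 3.5 doses on average, and 196/M = 6.44 months.

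| Doses in 28 weeks | On-treatment monthly average | Apparent change |
|---|---|---|
| 3 | 3D/6.44 = 0.466 D | −53% |
| 3.5 (long-run mean) | 3.5D/6.44 = 0.544 D | −46% |
| 4 | 4D/6.44 = 0.621 D | −38% |

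The middle row equals M/56. If the 4-week IV-free screening period is counted, the window is 84 days. The unchanged rate is then D × M/84 = 0.362 D per month, an apparent fall of 64%.

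**Oral iron, use unchanged, 7.4.2 scaling.**
- Baseline = 28d. On treatment = 196d/6.44 = 30.4375d. Ratio 30.4375/28 = 1.087, a false rise of 8.7%.
- Reduction threshold: baseline exceeds the EP average only if the true cut is more than 1 − 28/30.4375 = 8.0%.
- Over the treatment period, 8.0% of 196 days is 15.7 days. A constant user who stops for the last 15 days is therefore counted as not reduced.

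**If the 16-week divisor in 10.6.3 is used instead.** 112/M = 3.68 months.
- As the IV baseline, with a one-time dose counted once: D/3.68 = 0.27 D. Against 0.544 D on treatment this is a false doubling, not a fall.
- Applied to the 28-week totals, against the unscaled baselines: IV 3.5D/3.68 = 0.95 D against D (−5%); oral 196d/3.68 = 53.3d against 28d (+90%).
- Applied to EP oral iron: 28d/3.68 = 7.6d against 28d, so an unchanged user is classed as reduced.

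These three cases isolate the divisor. The duration rules printed beside it give zero days to any record starting on or after randomization, so that derivation cannot be run literally.

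**After scaling each baseline to M and using 7.4.2 throughout.** IV: D × M/56 = 0.544 D against 0.544 D. Oral: 28d × M/28 = 30.4375d against 30.4375d. Both false changes are 0%.

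**The case against.** The strongest reply is that the percentages are conditional. SAP 10.6.3 contains a second formula, labelled as a baseline, that contradicts 5.2.1, and the EP oral calculation is referred to that derivation and not to 7.4.2. On that text the errors differ in size and even in sign. This stands. A reader might infer that the SAP as written fixes a 46% fall, a 9% rise and an 8% threshold. The documents support those figures only if the 7.4.2 scaling governs.

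Second, a steady dose every 8 weeks is a device for the arithmetic and does not describe how IV iron is used in the trial. Protocol 7.7.1 limits IV iron after randomization to participants intolerant of oral iron or being evaluated for rescue. This also stands, and it is why a range is given. It does not remove the error, because an 8-week amount is not a monthly one whatever the pattern of use.

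Third, no IV change-from-baseline statistic is planned. Table 2.105 is titled as an on-treatment summary, and the layout of its shell is not in the text available. The false IV fall therefore appears only when the baseline and on-treatment summaries are read together, which 7.4.2 does plan to produce.

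Fourth, nothing in the documents suggests that oral cuts below 8% are common, so few participants may be misclassified.

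A reader might also infer that the comparison of on-treatment iron between arms is distorted. It is not distorted by this mismatch, which lies in the baseline values and is the same rule in both arms.

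**Conclusion.** The definitions are wrong as written: the baseline values are called monthly but are not on the SAP's month. Under the 7.4.2 scaling, baseline IV iron is overstated 56/30.4375 = 1.84-fold on the 8-week window, and baseline oral iron is understated by 8.0%. The 46% figure for IV iron assumes a steady rate of one dose per 8 weeks, with 38% to 53% for whole doses and 64% on the 84-day window. The oral figures assume a constant daily dose and that the EP average is also scaled as in 7.4.2.

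The importance is low. SAP 7.4 plans no testing of exploratory endpoints, and the effect is limited to within-arm reading of iron use and the oral-reduction count. Correcting the 16-week divisor alone would leave the baseline mismatch in place, so both need attention.

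**What to change.** 1. In SAP 5.2.1 and 10.6.3, define baseline monthly IV iron as total IV iron in the stated window × 30.4375/(window days). Use 56 for the 8 weeks before screening, or 84 if the 4-week IV-free screening period is included, and state which.
2. In the same sections, define baseline monthly oral iron as the 28-day total × 30.4375/28.
3. Use the scaled oral baseline in the reduction rule, for both the EP and the treatment-period counts.
4. Remove or reconcile the 16-week baseline formula in 10.6.3, and refer EP and Week 28 averages to the 7.4.2 scaling, so that baseline, EP and on-treatment values share one unit.

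The cost is two constants, one deleted or corrected formula, and the matching lines in the derivation program. No new data are needed.

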5. STUDY DESIGN

5.1. Overall Design

This is a 28-week, randomized, double-blind, placebo-controlled, parallel-group, multi-center Phase 3 study in participants with anemia associated with chronic kidney disease (CKD) who are not on dialysis. This study will enroll anemic participants who have a HemoCue Hgb 8.5 to 10.0 g/dL, inclusive. These participants will have limited history of IV iron and be rhEPO naïve prior to screening and randomization.

This study includes a 4-week screening period, a 28-week treatment period, and a 4-week follow-up period ([Figure 1](#)).

[figure not shown]
The total duration of study participation for each participant will be approximately 36 weeks.

Participants will be randomized 1:1 to receive either daprodustat or matching placebo tablets. Participants will not be provided with the results of their HemoCue Hgb assessment during their participation in the study.

Daprodustat and placebo doses for participants will be titrated based upon HemoCue Hgb. Dose modifications for these participants will follow a protocol-specified dose adjustment algorithm to achieve and maintain Hgb within the target range of 11.0 to 12.0 g/dL, inclusive. Dose changes will be made programmatically in a blinded fashion by the IRT system in order to ensure that investigators and participants stay blinded to the study treatment and the dose adjustments.

A rescue algorithm is provided to minimize participants having an inadequate response to the treatment for their anemia for an extended period of time and to enable rescue therapy to be provided to the participants based on local clinical practice. (Section 7.7.2)

Figure 1 Study Schematic

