| 
 • Date of last actual dose of randomized study treatment from the IP Discontinuation eCRF form. 
 ○ The dose steps used by the dosing algorithm described in the protocol include a dose hold or a zero dose. If participants are assigned by the algorithm to a zero dose, they do not receive randomized treatment for that period. Hence, it would be possible for a participant to complete the study, while still following the dosing algorithm, but not actually taking any actual randomized treatment. The last non-zero dose date then captures the latest date in the study that a participant physically took a dose of randomized treatment. • The eCRF allows for the possibility of partial or missing dates to be recorded for the last actual dose of randomized study treatment on the IP Discontinuation form (i.e., missing day, or day and month, or day and month and year). In such a case, or in case of a missing IP Discontinuation form, the following conventions will be applied in order to impute a last non-zero dose date: 
 ○ Missing day: 
 ▪ The last day of the month will be used, unless the treatment stop date also occurs in the same month; in this case, the treatment stop date will be used. ○ Missing day and month; 
 ▪ ‘31’ will be used for the day and ‘Dec’ will be used for the month, unless the treatment stop date also occurs in the same year; in this case the treatment stop date will be used. ○ Missing day, month, and year: 
 ▪ Treatment stop date will be used only for participants who have a non-missing treatment start date. |

CONFIDENTIAL

205270

| |
|---|
| General |
| Treatment Stop Date |
| 
 Calculated as the latest randomized treatment dose stop date. The eCRF does not allow for the possibility of missing or partial dates to be recorded for the dose stop date on the study treatment form |
| End of Treatment Value |

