| 
 In order to calculate the average monthly IV iron dose from Randomization to Week 28, the dose of IV iron will be standardized to obtain a continuous single unit IV iron dose in terms of mg/month for the period from the Randomization date to the Week 28 visit date while the subject is on treatment. 
 Note: Participants who are randomized but never treated will not have a value for average monthly IV iron from Randomization to Week 28. The time period starts with treatment start date, instead of randomization date. [missing treatment start date are excluded] If the treatment end date [non-zero dose] is prior to the Week 28 date, then that is used instead. The last non-zero dose date is used for Dapro, treatment end date used for Placebo. IV iron therapy concomitant medication records that occur or are ongoing during the period from the participant's Day 1 visit date to the Week 28 visit date will be selected and ordered by start date and end date. The standardization will be carried out with the following formula: 
 Standardized IV iron dose (mg/week) = IV iron drug dose (mg) * frequency | | | | | | | | | | | | | | | | | | | | | | | | | | | | | | | | | | | | | | | | | | |
| Note: Frequency and Gap Factors defined as follows: | | | | | | | | | | | | | | | | | | | | | | | | | | | | | | | | | | | | | | | | | | |

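### The average monthly iron window ends at a different date in each arm, so a participant whose treatment ends in a dose hold can get a different value by arm label alone

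*SAP*

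**What the plan says.** SAP 10.6.3 defines average monthly IV iron from randomization to Week 28 over a window that starts at the treatment start date. On the end of the window it says first: "If the treatment end date [non-zero dose] is prior to the Week 28 date, then that is used instead". It then adds: "The last non-zero dose date is used for Dapro, treatment end date used for Placebo". Oral iron is tied to the same derivation: "The calculation of the average monthly oral iron from Randomization to Week 28 will follow the calculation of the average monthly IV iron". The Week 24 to 28 oral average follows it too, with the start moved to the Week 24 date. That second average feeds the count of participants who reduced oral iron during the evaluation period, which requires a non-missing value.

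Elsewhere the SAP does not separate the arms:

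- SAP 7.4.2 (Iron Parameters) takes iron given while on randomized treatment and finishes by "dividing by (the number of days the participant was on randomized treatment/30.4375 days", with no mention of arm.
- SAP 10.6.1 defines the last non-zero dose date as "Date of last actual dose of randomized study treatment from the IP Discontinuation eCRF form" and the treatment stop date as "Calculated as the latest randomized treatment dose stop date". Neither definition refers to arm.
- SAP 10.6.1 uses the treatment stop date plus one day for the end-of-treatment value of iron parameters and oral iron. SAP 10.6.2 uses the treatment stop date for extent of exposure.
- SAP 10.4.1.3 classifies concomitant medication as on-treatment up to the last non-zero dose date plus one day, again for everyone.

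The two dates part company because of dose holds. SAP 10.6.1 explains: "If participants are assigned by the algorithm to a zero dose, they do not receive randomized treatment for that period". Holds are not confined to one arm. Protocol 5.1 states: "Daprodustat and placebo doses for participants will be titrated based upon HemoCue Hgb", and Protocol 7.2 applies the adjustments, including the hold, to both arms through the IRT system.

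**The concern.** The window end decides which iron is counted and how many days it is divided by. If that end depends on the treatment label, part of any between-arm difference can come from the derivation and not from treatment. When treatment ends in a hold, the iron and days in the hold are dropped on daprodustat and kept on placebo. No reason is given, and nothing elsewhere in the SAP cancels the rule.

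At stake are Tables 2.102 to 2.105: average monthly oral and IV iron, and the counts of participants who reduced oral iron. A programmer working from SAP 7.4.2 and one working from SAP 10.6.3 could also get different answers for the same daprodustat participant.

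**Working it through.** The plan gives no figure that depends on this rule, so there is none to reproduce. The check is to give one iron and dosing history first one arm label and then the other.

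**Inputs.** Average monthly iron = total mg / (window days / 30.4375), from SAP 7.4.2. Window end by arm, from SAP 10.6.3; I read its treatment end date as the treatment stop date of SAP 10.6.1. Illustrative assumptions: treatment starts on Day 1 and stops on Day 196 (28 × 7), the Week 28 visit is not earlier than that, and the terminal hold runs to the stop date.

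**One IV dose of 200 mg at Week 4, last non-zero dose on Day 140.**

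- Daprodustat label: 200 / (140 / 30.4375) = 43.5 mg/month.
- Placebo label: 200 / (196 / 30.4375) = 31.1 mg/month.
- Ratio: 196 / 140 = 1.40.

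**How it varies with the start of the hold.** For one dose given before the hold, the ratio is 196 divided by the days to the last non-zero dose, whatever the dose size. With 1000 mg:

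| Terminal hold from | Days to last non-zero dose | Daprodustat label (mg/month) | Placebo label (mg/month) | Ratio |
|---|---|---|---|---|
| Week 12 | 84 | 362.4 | 155.3 | 2.33 |
| Week 16 | 112 | 271.8 | 155.3 | 1.75 |
| Week 20 | 140 | 217.4 | 155.3 | 1.40 |
| Week 24 | 168 | 181.2 | 155.3 | 1.17 |
| No terminal hold | 196 | 155.3 | 155.3 | 1.00 |

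**Direction, using oral iron of 100 mg/day and a hold from Week 24.**

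- Taken throughout: 3043.75 mg/month under both labels.
- Stopped when the hold starts: 3043.75 on daprodustat; 100 × 168 / (196 / 30.4375) = 2608.9 on placebo.
- Taken only during the hold: 0 on daprodustat; 100 × 28 / (196 / 30.4375) = 434.8 on placebo.

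Iron before the hold therefore raises the daprodustat value relative to placebo, iron only during the hold lowers it, and a constant rate gives no difference.

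**Week 24 to 28 oral iron.** With a hold from Week 24 or earlier, the daprodustat window has essentially 0 days, so the average is undefined and the participant drops out of the evaluation-period reduction count. The same participant on placebo keeps 28 days. Under Protocol 7.2 a hold follows a confirmed Hgb of 13 g/dL or more, or a decrease called for at the lowest dose, so this loss would be related to Hgb.

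**With one end date.** For the 1000 mg case with a hold from Week 24, both labels give 155.3 on the treatment stop date, or both give 181.2 on the last non-zero dose date. The difference disappears either way.

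**A limit of the check.** The record-level formulas printed later in SAP 10.6.3 do not use this window. Their stop date is capped at the day before randomization, and their divisor is fixed at (16 × 7) / 30.4375 = 3.68 months and labelled as baseline. They describe a pre-randomization period, so the figures above rest on SAP 7.4.2 together with the window sentences.

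**The case against.** The strongest reply is that this changes little. SAP 7.4 plans no testing of exploratory endpoints, and average monthly iron is one of several iron summaries, alongside time to first IV iron, frequency and dose of IV iron, ferritin, TSAT and hepcidin. The arms diverge only when treatment ends in a hold. The Day 140 example needs an eight-week hold, and a placebo participant who entered at 8.5 to 10.0 g/dL may seldom reach one. Measured against the concomitant medication rule in SAP 10.4.1.3, the sentence alters essentially only placebo participants who end in a hold. All of this stands as a limit on size, although the rarity is an assumption because the documents give no frequency.

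A possible defence of the rule is that placebo has no non-zero dose. The documents do not say so. SAP 10.6.1 defines the date by the last actual dose of randomized treatment, Protocol 7 counts placebo as study treatment, and the SAP already applies the date to both arms for adverse events, blood pressure and laboratory data. It is true that SAP 10.6.1 allows the last dose date to be partial or missing, so it is not guaranteed to be recorded for everyone, but its imputation rules are also the same in both arms.

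A reader might infer that the rule favours daprodustat, or that 40% estimates the bias in the arm means. The documents support neither: the direction depends on when iron is given, and the share ending in a hold is not stated. A reader might also see a threat to the blind because the derivation needs the treatment code. SAP 3.2 places the final analyses after the codes are distributed, so that adds little.

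**Conclusion.** The point holds within limits. As written, the window end depends on the arm, and a participant whose treatment ends in a dose hold before Week 28 can get a different IV or oral iron average by label alone. For a single dose before the hold, the ratio runs from 1.17 (hold from Week 24) to 2.33 (hold from Week 12). For the Week 24 to 28 oral value, the difference can be between an undefined value and a full 28-day window. These are results for single illustrative participants under the stated assumptions, not estimates of the effect on the arm means, which cannot be calculated from the documents.

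The effect is confined to exploratory, untested summaries. The primary and principal secondary analyses do not use these values. The change is still worth making because the rule has no stated rationale, conflicts with SAP 7.4.2, and is cheap to remove.

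**What to change.** In SAP 10.6.3, delete the arm-specific sentence and the bracketed reference to non-zero dose in the sentence before it; deleting only the first would leave the text pointing to the wrong date. Define the window end as the treatment stop date, capped at the Week 28 visit, in both arms, for IV and oral iron and for Tables 2.102 to 2.105. This agrees with SAP 7.4.2, with the end-of-treatment convention for oral iron in SAP 10.6.1 and with exposure in SAP 10.6.2. State the same rule in 7.4.2 and 10.6.3, and say that it replaces the concomitant medication convention of SAP 10.4.1.3 for these endpoints.

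Using the last non-zero dose date in both arms would also remove the dependence on arm, but it would keep the undefined Week 24 to 28 values.

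In the same edit, align the record-level stop date and the divisor in SAP 10.6.3 with the chosen window, since as printed they cannot produce a post-randomization average. The cost is a few lines of SAP text and a small programming change, with no new data.
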